## **7.2 Intervention Components**

### **7.2.1. Policy-level components.**

The intervention framework is highly dependent on the identification and engagement of worksite administrators and managers to enact policy-level workplace modifications, implement robust environmental changes (e.g., sit-stand workstations), and to model and promote behavior change. Therefore, a required item will be to identify a worksite leader and advocate(s). A leader is defined as a person holding a higher-level management position to which the department, division, or unit employees report. The primary role of this individual will be to provide higher-level support for intervention strategies to be implemented. Primary responsibilities will be to determine appropriate Toolkit items, encourage participation in worksite initiatives, and approve potential policy changes. An advocate is defined as a person who plays an active role with study participants and will work closely with the Stand & Move at Work study team to implement the selected changes. Advocates will be considered the primary

contact to link worksite employees, management, and the study team. Primary responsibilities will include aiding the implementation of strategies agreed upon by higher-level management. Organizational changes will be reinforced by the distribution of four quarterly support emails sent by the leader to employees in the workgroup. Templates will be provided to minimally include: (a) support for the program and employee participation; (b) a brief review of the previous quarter progress; (c) commendation of individuals who have shown high levels of engagement; and (d) an outline of new intervention initiatives for the upcoming quarter. Leaders will also formally agree to allow employees up to 5 min breaks every hour. Shared leader and advocate responsibilities will include quarterly meetings with an experienced behavioral science research team member who will be the designated worksite coordinator throughout the study to review past progress and plan for the coming quarter using the Toolkit as a guide. The aim of the research team member is to facilitate the intervention by ensuring all materials and concepts are explained fully explained, it is not to actively lead the intervention. As such, all team members will have extensive knowledge of the Stand and Move Toolkit to provide the leaders and advocates with support. Successes and challenges from the previous quarter will be discussed and each worksite will be encouraged to implement a new strategy to maintain or potentially increase employee interest in the program. Similarly, all worksite leaders and advocates will be invited to join a monthly *STAND+* and *MOVE+* conference call with the study principal investigators. These will serve several purposes: (a) to provide opportunities for other worksites to share and learn from other worksites within the same randomized study arm; (b) to document worksite participation, progress, and new strategies; and (c) to provide insight into the breadth and scale of the study to reinforce participation from a scientific and health-based perspective.

### **7.2.2. Environment-level components.**

The primary environmental difference between the *STAND+* and *MOVE+* study arms will be the installation of a sit-stand workstation for the *STAND+* arm only. The workstations will be installed by our trained research staff, as well as worksite-specific ergonomic and wellness professionals. The Ergotron sit-stand workstation Workfit-TL model (Ergotron, Inc., St. Paul, MN) has been selected because it is able to be retro-fitted for use with almost all workspaces, requires little or no installation as it is simply placed on the existing desk surface, is affordable relative to many alternatives, has more desk surface area than many alternatives on the market, it can be easily raised and lowered to a broad range of positions, and can accommodate one or two large computer monitors. The Workfit-TL transitions from seated to standing positions by holding two levers and providing minimal force. Prior to installation a workspace inventory will be conducted for each participant to identify any potential barriers to use such as overhead shelving, insufficient computer cabling, or fixed keyboard trays. To eliminate these barriers, overhead shelving will be moved by worksite facilities management, cable extenders added (if needed), and additional wireless keyboards will be provided to those with keyboard trays so that participants are not required to move their existing keyboards with each sit-stand transition. The same Ergotron Workfit-TL will be installed at the 12-month time point for all *MOVE+* arm participants. All participants will receive ergonomic instructions for both sitting and standing postures via the e-newsletter and will undergo a coaching session at the time of installation.

Other required environmental changes will include a signage starter pack that is designed to (a) provide information about the behavior; (b) provide information on benefits of action (e.g., benefit of taking the stairs); (c) encourage goal setting (e.g., “make this a standing meeting”); (d) provide general encouragement (e.g., “we stand for health”); (e) provide instruction (e.g., walking routes around the office space); and (f) serve as visual cues. Signage will also demonstrate organizational support for the program and intent to change the cultural norm. Walking routes will be created for each worksite to reinforce the behavioral targets listed above. Typical routes will include alternative restrooms, centralized printing and trash can areas, and indoor and outdoor (if possible) perimeter routes. The distance per route and estimated number of steps will be provided on the signage. Advocates will be encouraged to place walking routes in communal and prominent areas throughout the worksite. All participants regardless of randomization will be provided with a footrest. The footrests will serve the following three purposes: (a) as a resting position for either foot while both seated and standing; (b) as a stretching aid (gastrocnemius and soleus); and (c) as a visual reminder regarding participation in the program. Leaders and advocates may also wish to implement additional optional environmental changes throughout the program via combined environmental, individual, and social strategies. For example, a prominent and interactive communal board to promote the Stand & Move at Work program (termed an “Ideaboard”) or implementing environmentally based worksite challenges (e.g., centralized printing only challenges). Ideaboard templates and example challenges will be provided in the Toolkit.

### **7.2.3. Individual- and social-level components.**

An e-newsletter (The Insider) will provide a regular and direct medium for delivering individual- and social-level intervention content. The Insider will incorporate both individual (e.g., goal-setting) and social elements (e.g., quizzes and worksite social announcements). The Insider will be sent weekly during the first month of the intervention to facilitate transition and encourage early engagement. During months 2–12, the Insider will be sent bi-weekly, and a total of 26 newsletters will be sent. See Table 2 for a list of Insider topics. The content has been developed and designed by behavioral scientists and worksite wellness professionals to target 25 out of the 26 components of the behavioral taxonomy wheel. Motivational interviewing will be the only component not targeted, given the need for face-to-face interaction. The Insider will be coordinated with and reinforced by additional complementary organizational, environmental, and social components. Other individual level strategies will include a 1-on-1 coaching session to identify specific goals and behavior change strategies relating to the key intervention messages. Using a goal setting sheet, participants will be encouraged to record and display their goals within daily eyesight. Participants will also receive instructions regarding the deskbased ergonomic set up (both *MOVE+* and *STAND+*). The *STAND+* arm will receive specific instructions (guided by an experienced ergonomist) regarding their new sit-stand workstation set up. Key messages will include switching position regularly and gradually increasing standing or LPA time. Social strategies (i.e., formation of walking or stretching groups) may be endorsed by leaders via support emails, actively led by advocates, or promoted via additional signage and Ideaboard content. Due to the variation in worksite culture, job demands and environmental challenges, it is expected that new ideas and variations of the

suggested Toolkit items will emerge. This will be discussed and documented during the quarterly meetings and quarterly audits. The required multi-level tactics show reinforcement of behavior change across the social-ecological spectrum, utilizing all aspects of the behavior change taxonomy wheel. This integrated approach shows promise for shifting the cultural norm within a workplace from reinforcing highly sedentary, seated behavior patterns to one where standing and moving is expected, rewarded, and celebrated. This cultural shift is necessary to produce sustainable, long lasting changes that are likely to impact health and well-being on a large scale.

Both *STAND+* and *MOVE+* worksites received the same multi-component intervention toolkit targeting organizational, environmental, cultural, and social changes within the workplace. Examples organizational changes included: (a) installation of sit-stand workstations (b) quarterly support emails, (c) ergonomic support and (d) bi-weekly e-newsletters. Examples of Environmental changes included: walking routes, (b) signage, (c) waste and recycling bin reallocation, (d) use of centralized printing areas, (e) inviting stairways and an (g) ideaboard. Examples of cultural and social changes included (a) allowance of 5-min breaks every hour, (b) promotion of face-to-face interaction, rather than email, (c) standing meetings, (d) walking meetings, (e) stretch breaks), (f) contests), and (g) social groups.

### 7.3 Difference between Intervention Arms

The primary study arm differences will be implemented at the environmental level with the provision of a sit-stand desk at the start of the intervention for the *STAND+* group only. This primary difference will require small adaptations to other intervention strategies. First, participant goals will differ per arm to reflect the different arm intervention goals (i.e., increasing standing and LPA time for *STAND+* vs. increasing LPA only for *MOVE+*). All participants will be encouraged to adhere to a '30-min rule', however, the meaning of this target rule will differ per arm. For the *STAND+* group this will be communicated as achieving a 30:30-minute sit to stand ratio to ultimately replace half their sit time with a combination of standing and moving at work. For the *MOVE+* group this will be communicated as replacing 30 min of sit time with an equal accumulation of moving more throughout the work day. The 1-on-1 sessions held at the start of the program will facilitate specific goal setting at the individual level to help achieve the '30-minute rule' per arm. Consequently, the strategies communicated during the 1-on-1 session and throughout the study duration will differ slightly per arm (see Table 3).

Second, although the *STAND+* and *MOVE+* arms will be provided with an identical Stand & Move Toolkit and the same level of support to implement socio-ecological changes, it is likely that the application of the Toolkit will differ per arm to target the specific target intervention arm goals. Finally, in some instances, the e-newsletter topics will remain the same across arms but the content will be adjusted per arm to reduce contamination and ensure that information is specific to the intervention arm. For example, the ergonomically themed e-newsletter will include sit-stand desk information for the *STAND+* group, however, the *MOVE+* content will only include seated desk information. Stand & Move intervention support for *STAND+* will cease following the 12-month assessment period. However, *MOVE+* participants will receive a sit-stand desk and ergonomic advice at the 12-month time point, and after which no additional intervention

support will continue post-installation. Both arms will still have access to the Toolkit during this follow-up period (12–24 months).

### 8. Collecting Worksite Data

Worksite level data will be collected in conjunction with in-person (or by phone as a last resort) Quarterly meetings held with each worksite. These meetings will be held at Baseline, prior to the start of the intervention, 3-months, 6-months, 9-months, and a final meeting at 12-months.

Data collected at each of these time points will include:

- Planned intervention activities
- Completed intervention activities
- Successes or barriers of intervention activities
- *Quarterly Audit Survey* that asks about various organizational and individual level activities, events, resources, and facilities.

### 9. Collecting Participant Data

Participant level data will be collected in four time points, including baseline, 3-months, 12-months, and 24-months. Participants will be scheduled for fasting visits held in the morning at their respective worksites. As two worksites will be recruited to start the intervention at the same time, with collection dates being within one week of each other, participants can opt to attend a visit at the other worksite.

Data collected at the in-person fasting visit will include:

- Blood pressure
- Height (baseline only)
- Weight
- Pregnancy status (biologically females only)
- Fasting venous blood draw

An activPAL will be affixed to the right leg of each participant at the visit; this placement will be rescheduled if the participant will be out of the office for the majority of the upcoming week.

Daily surveys will be administered in conjunction with the activPAL wear. These logs will assess both daily sleep and work times and be sent via Qualtrics each morning for seven days.

Along with the in-person visit and activPAL wear, a main study survey will be sent out during each assessment period (baseline, 3-months, 12-months and 24-months). This survey will be used to collect demographic characteristics as well as information regarding sleep, diet, physical activity, and overall health.

### 10. Measures

All measurements will be taken at baseline and 12 months, with additional interim measurement at 3months and follow-up at 24 months. All questionnaires will be administered via Qualtrics (Salt Lake City, UT)

### 10.1 Blood Pressure

Blood pressure will be measured with the Omron BP742 automated machine and the Omron HEM-RML30 cuff (Omron Healthcare Inc., Lake Forest, IL) three times following 5 min of quiet sitting, with 30 s in between each measurement. The lowest two measures of diastolic and systolic blood pressures will be averaged for final blood pressure values.

### 10.2 Anthropometrics

Standing height will be measured in centimeters (cm) using a portable height board (SECA). Prior to the height measurement the participant should remove his/her shoes. If the subject has a hair accessory or hairstyle that interferes with the measurement, she/he will be asked to remove the accessory or change her/his hairstyle (e.g. take out ponytail band) if possible (some hair styles/accessories are difficult to remove or costly to replace, and these styles may be left in place).

- (a) Participant must stand erect with his/her back towards the stadiometer. The weight of the participant must be evenly distributed on both feet and the arms hang freely by the sides of the body, palms facing the thighs. The participant should place the heels together, with both heels touching the base of the vertical board. The feet should point slightly outward, at about 60° angle. Note: If the subject has knock-knees, the feet are separated so that the medial borders of the knees are in contact but not overlapping.
- (b) The subject's head should be positioned in the Frankfurt Horizontal plane. In this position an imaginary line can be drawn from the bottom of the eye socket (orbital margin) to the external opening of the ear (external auditory canal).
- (c) The heels, shoulder blades, buttocks, and back of the head should be against the vertical surface. Note: The heels, buttocks, scapulae, and posterior aspect of the cranium (head) of some subject cannot be place in one vertical plane while maintaining a reasonable natural stance. These subjects are positioned so that only the buttocks and the heels or the cranium are in contact with the vertical board.
- (d) The participant should be asked to inhale deeply and hold his/her breath, while maintaining the erect position and without altering the load on the heels. Reposition the head in the Frankfurt plane, if necessary. The moveable headboard should be brought onto the highest point of the head, with sufficient pressure to compress the hair.
- (e) If the participant is notably taller than the study staff member responsible for recording the reading, she/he should use a step stool to view the measurement.
- (f) The measurement is recorded to the nearest 0.1 cm. The measurement is called out by the measurer as follows: "height, 162.5" and repeated "162.5" as he/she writes down the number on the Anthropometry Form. The participant is asked to step away and then step back into the same position for a second measurement.
- (g) Repeat the process and record the second measurement in the 'Trial B' column of the height section of the Anthropometry Form.
- (h) If the first and second measurements differ by >1 cm repeat the measurements, a third measurement will be taken.

Any conditions or situations, which occur to make the measurement undependable on the bottom of the form. (e.g. subject couldn't or refused to comply with the removal of hair accessory, wouldn't remove shoes, etc.) will be noted.

Body weight will be measured in kilograms (kg) using a Tanita TBF-300A Total Body Composition Analyzer. The Tanita scale also allows for the calculation of percent body fat utilizing bioelectrical impedance. All participants will be queried about the presence of any medical device that would be impacted by the small electrical current. Only weight measures will be taken for those endorsing the presence of such devices.

- (a) The participant will be asked to remove shoes, any coat or cardigan, and empty his/her pockets.
- (b) The participant will stand in the center of scale, facing away from the balance, holding the head up. Body weight must be evenly distributed on both feet and the participant must have his/her hands hanging freely at his/her sides (i.e. make sure participant is not holding on to anything).
- (c) Weight is measured and recorded to the nearest 0.1 kg.
- (d) The body fat percentage will be displayed after a short pause, and should be recorded.
- (e) Have the participant step off the scale, and then repeat steps a-d, and record the second weight/body fat percentage.
- (f) If the first and second measurements differ by  $> 0.2$  kg repeat the measurements, a third measurement will be taken.

Any conditions or situations, which occur to make the measurement undependable, should be noted on the bottom of the form.

### 10.3 ActivPAL

Our primary outcomes, time spent sitting and LPA at work, will be assessed with the activPAL3 micro accelerometer (PAL Technologies, Glasgow, United Kingdom) for seven consecutive days at each measurement time point. The activPAL will be waterproofed using medical grade adhesive covering and attached to the midline of the thigh using a breathable, hypoallergenic tape. This method allows for the monitor to be worn continuously for seven consecutive days without removing for bathing or other water-based activities (a valuable feature that reduces missing data). Additional adhesive dressing will be given to all participants for re-application as necessary. The primary outputs of the activPAL are time spent sitting, time spent upright, and time spent "stepping." Participants concurrently will complete an online daily log where they will report their sleep/wake schedule and time arriving and departing their workplace. The daily logs will be used to filter time spent sitting and LPA during work hours. In addition, any uninterrupted sedentary bouts of more than 6 h that occur within reported wake times will be considered non-wear times and treated as missing data. Days with  $<10$  h of monitor wear data or  $<4$  hours of reported work time as monitor wear data will be excluded from analyses. Outcomes will be reported as a standardized 8 h workday to account for differences in total work time. Full details of activPAL initialization, wear, and download protocol are in Appendix 1.

### 10.4 Venipuncture

Participants will be instructed to fast for nine consecutive hours prior to each blood draw. Blood will be drawn from the antecubital vein into EDTA vacutainers, and plasma will be stored at  $-80^{\circ}\text{C}$  until analysis in batch. Samples from the Phoenix site will be shipped to UMN on dry ice periodically for batch-processing. Biomarker analyses will be conducted by the Advanced

Research and Diagnostic Laboratory at the University of Minnesota, Minneapolis, MN, using a Roche COBAS 6000 chemistry analyzer (Roche Diagnostics, Indianapolis, IN). Plasma glucose will be measured by the hexokinase method (interassay CV = 1.3% at 97.2 mg/dL, 1.8% at 223.3 mg/dL). Plasma HDL-C will be measured by the modified direct enzymatic approach (interassay CV = 3.2% at 27.0 mg/dL, 1.9% at 51.7 mg/dL). Plasma triglycerides will be measured with the GPO-Trinder kit (Roche Diagnostics, Indianapolis, IN; interassay CV = 2.0% at 112.4 mg/dL, 2.3% at 195.8mg/dL). Plasma insulin will be measured with a sandwich immunoassay using electrochemiluminescence (Roche Diagnostics, Indianapolis, IN; interassay CV=3.1% at 121.2 pmol/L, 3.1% at 377.9 pmol/L).

## 11. Data Management

### 11.1 In-person Visit Data

In person visit data, including anthropometrics, blood pressure, and whether venous blood draws were successful will be collected on paper forms. These forms will be kept in secure, locked filing cabinets and entered into Qualtrics.

### 11.2. Survey Data

All survey data will be collected via Qualtrics. Qualtrics is a secure, web-based platform for designing, collecting, and securing survey data. All survey data will be stored on encrypted servers.

### 11.3 ActivPAL Data

ActivPAL data will be extracted and stored on secure study servers at each site. The University of Minnesota will upload this data to BOX for retrieval by ASU, who will be the primary site to compile, clean, and process this data.

### 11.4 Data Integrity

All clinical assessment data will be double entered. All blood data will be examined for computational value errors associated with out-of-range variables. All data will be examined for outliers and improbable values.

## 12. Data Analysis Plan

### 12.1 Data analysis.

Threats to internal validity (e.g. contamination, envy) preclude randomization of individuals within the same worksite; hence, a group randomized trial is being conducted [54]. Such a trial involves randomization of worksites with members within a worksite being assigned to the same experimental condition. Hierarchical linear (or generalized linear) models will be used to provide valid estimates of the intervention effect and its variance (for generating the test of statistical significance). Because the number of sites is limited by feasibility, the asymptotic balance of all measured and unmeasured confounders is not applicable, and hence it is important to randomize worksites within small blocks (or pairs) of matched worksites with similar characteristics likely to affect the outcome measure. Because our goal is to enroll 12 worksites in the Phoenix area and 12 in the Minneapolis area, we will stratify the randomization scheme

on geographical location so that we will not have any confounding by geographical location (AZ vs. MN). We will identify six pairs of sites in AZ and six pairs in MN, with the pair members having the same sector (academia, government, or healthcare/industry). Each pair will be randomized so that one worksite in each pair is assigned to the *MOVE+* intervention and the other in that pair assigned to the *STAND+* intervention. One of the site PIs and a Biostatistician at the University of Minnesota will be responsible for the randomization. Randomization will occur immediately following the baseline data collection for both sites. The PI will notify the biostatistician when there are two matched worksites ready for randomization. The two worksites will be ordered as “First” and “Second” depending on the calendar dates of the baseline data collection. The statistician, with no knowledge of the worksites, will use a coin flip to assign the two worksites to the *STAND+* or *MOVE+* interventions. Initial analyses will provide descriptions of the baseline frequencies and means (SD) of characteristics by worksite and by experimental condition. Statistical testing of differences in baseline characteristics is not necessary, but will provide assurance that the randomization has not produced a grossly unbalanced assignment. If the distributions of our outcome variables are not normally distributed, we will log-transform the outcome data. Our primary hypotheses will be tested by invoking a repeated-measures hierarchical linear model of the experimental contrast between the two conditions of the 12-month measure of LPA (min/ 8-h) and sitting (min/8-h), respectively. Because total time is standardized to 8 h, we will also express our outcomes in percent of time in LPA and sitting. A repeated measures hierarchical analysis will be conducted. The covariates expected to include are age, sex, body mass index, and the baseline values of the dependent variables (e.g., sitting time, LPA, and metabolic risk score). The resulting estimate and its standard error provide a t-statistic based on  $2(g-1)$  degrees of freedom (df), where g represents the number of worksites per experimental condition [54]. A similar analysis will examine the secondary hypothesis for the metabolic risk score. Other outcomes, including sit-stand transitions, will use hierarchical generalized linear models with a log link. The analysis approach for process (3 month) and maintenance (24 month) outcomes will be similar. In terms of missing data, sensitivity to member-dropout is small; if on average only 85% are followed, the detectable effect sizes increase by a factor 1.05. Worksite dropout would be a major threat to validity, but that is highly unlikely to occur. Baseline characteristics of those not providing follow-up data will be examined to assess whether these are non-informative missingness. Under the assumption that dropout is not related to the measures that would have been collected, the analysis of the data excluding dropouts is unbiased.

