#### 4.2. Timeline

Participating worksites will be recruited as pairs within a single sector at each worksite utilizing a rolling recruitment method. We will also rotate the enrollment of sector pairs over the seasons of the full calendar year to help avoid seasonal effects, beginning with the first two pairs enrolled in January 2016 and the final two pairs enrolled in November 2016. Enrolling two pairs every other month will also alleviate logistical and labor burdens for recruitment, data collection, and intervention implementation.

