## 6. Randomization

Randomization to either the *STAND+* or *MOVE+* intervention arms of the trial will be at the level of the worksite. Randomization will be stratified on the three sectors nested within each of the two regions (Phoenix, AZ and Minneapolis/St. Paul, MN). Within each region, eligible worksites will be enrolled in pairs matched on sector, and each matched pair will be randomized so that one is randomized to receive the *STAND+* intervention with the other receiving the *MOVE+* intervention. This scheme will ensure a balanced design by both region and sector.

Randomization will not occur until all four worksites in the recruitment wave (2 per region) have completed their baseline assessments. Therefore, a participant will be considered enrolled in the active intervention once they have consented, completed baseline assessments, and paired worksites have been randomized to study arm. Prior work by our research team has suggested that we should expect 40%–75% participation within the identified worksite, which based upon worksite size will approximate our target recruitment of N = 720 participants.

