
### 12.2 Power Analysis

We aim to enroll 24 worksites ( $N=12$  per condition) evenly distributed across Arizona and Minnesota with on average 30 employees per worksite (Total N members = 720 employees). In a baseline-adjusted analysis, let D represent the minimal detectable intervention effect, g the number of worksites per experimental condition, m the average number of members per worksite,  $S_2$  the member variance,  $T_2$  the work-site level variance,  $r_m$  and  $r_g$  the member and work-site correlations over time respectively, and  $t(d, a/2)$  and  $t(d, p)$  the critical t-statistic values based on d df for  $a/2$ =Type I alpha level (2-sided) and  $p$ =power. Then the minimal detectable difference is  $D_2 = (t(d, a/2) + t(d, p))^2 (S_2(1 - r_{2m})/m + T_2(1 - r_{2g}))^2 / g$ . Dividing by  $S_2$  yields the square of the Effect Size (ES) and  $T_2/S_2$  is the variance components ratio (VCR). In the unlikely

situation where the  $g$  are unequal, replacing  $2/g$  by  $(1/g_0+1/g_1)$  will lead to a minimal increase in  $D$  unless the  $g$  are grossly unequal. With  $g=12$  (worksites per condition),  $d=22$ , and  $N=720$ ,  $m=30$ ;  $\alpha/2$  is set to 0.025 and power is set 80%. The detectable effect sizes for this trial range from 0.21 to 0.26 across the three outcomes, which are relatively small effects, and thus we are well powered in this study. On an absolute scale, as also shown in the table, we will be able to detect a difference between intervention arms as small as 12.2 min/8-hr work day of LPA and 14.6 min/8-hr work day of sitting time. Our preliminary studies clearly demonstrate our ability to achieve these effects: (a) For LPA; the crossover study (12) showed a 38.4min/8-hr workday increase (other two studies did not target LPA or did not use a monitor designed to detect LPA); (b) for sitting, both the crossover and natural experiment showed >30min/8-hr workday reductions; and (c) for cardiometabolic risk, all 3 studies showed moderate to large effect sizes. This study is powered well to detect effects that are considerably smaller than what we have observed in our preliminary studies

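### Region, sector and pair shape the randomisation but are absent from the primary model and its 22 degrees of freedom

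*Combined protocol and SAP*

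**What the plan says.** Section 6 sets the design: "Randomization will be stratified on the three sectors nested within each of the two regions". Section 2.1 plans four worksites per sector per region, so there are six strata with two pairs each and 12 pairs in all. A coin flip sends one member of each pair to each arm (section 12.1). The stated aim is balance: "This scheme will ensure a balanced design by both region and sector". Section 12.1 also says that the blocks are made of "matched worksites with similar characteristics likely to affect the outcome measure".

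The primary analysis is a repeated-measures hierarchical linear model for LPA and for sitting. On its terms, section 12.1 says: "The covariates expected to include are age, sex, body mass index, and the baseline values of the dependent variables". On the test, it says: "The resulting estimate and its standard error provide a t-statistic based on" 2(g − 1) df, with g worksites per arm. Section 12.2 takes g = 12 and d = 22. No section places region, sector or pair in the model.

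**The concern.** Matching within strata makes the true variance of the arm difference smaller, because stratum effects appear equally in both arms and cancel. An analysis without the strata does not see this. It treats stratum differences as noise between worksites and reports a standard error that is too large.

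If region and sector remain prognostic after baseline adjustment, both primary tests reject too rarely under the null, their confidence intervals are too wide, and some power is given up. The estimate itself is not biased. The plan also leaves open what the analyst should do: adding the strata later contradicts the written df, and leaving them out ignores the design.

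**Working it through.** **Degrees of freedom.** 2(12 − 1) = 22 reproduces the plan's figure. It equals 24 worksites less two arm means, so no worksite-level term has been counted. Six strata leave 24 − 2 − 5 = 17, region plus sector main effects leave 24 − 2 − 3 = 19, and pairs leave 11. The multiplier in the detectable difference is t(0.975) + t(0.80):

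| Model | df | Sum of t values | Ratio to plan |
|---|---|---|---|
| As planned | 22 | 2.932 | 1 |
| Region + sector | 19 | 2.954 | 1.007 |
| Six strata | 17 | 2.973 | 1.014 |
| Pairs | 11 | 3.077 | 1.049 |

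**Worksite share of the contrast variance.** The variance inputs of section 12.2 are not in the text available, so the share is inferred from section 12.1: "if on average only 85% are followed, the detectable effect sizes increase by a factor 1.05". Follow-up of 85% divides only the member part of the variance by 0.85. With member share p, 1.05² = 1 + p(1/0.85 − 1), so p = 0.1025/0.1765 = 58% and the worksite share is 42%. If 1.05 was rounded from 1.045 to 1.055, the worksite share is 48% to 36%. The plan's formula is baseline-adjusted, so this is a share of the residual variance.

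**Overstated standard error.** Let strata explain a share s of the worksite part (assumed; not in the documents). Set the total variance of a worksite mean to 1. The part that governs the arm difference is 1 − 0.42s. The within-arm sum of squares still picks up 20/22 of the stratum variance 0.42s. The ratio of estimated to true standard error is √[(1 − 0.42s + 0.42s × 20/22)/(1 − 0.42s)]:

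- s = 10%: √(0.996/0.958) = 1.02
- s = 30%: √(0.989/0.874) = 1.06
- s = 50%: √(0.981/0.790) = 1.11

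**Type I error and power.** These come from a simulation of 24 worksite means, with a coin flip within 12 pairs, two pairs per stratum, a 42% worksite share and 100,000 trials per case. Power is at the plan's stated detectable difference.

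| Stratum share s | Type I, 22 df | Type I, strata (17 df) | Power, 22 df | Power, strata |
|---|---|---|---|---|
| 0% | 4.9% | about 5% | 80% | 79% |
| 10% | 4.6% | about 5% | 80.7% | 80.8% |
| 30% | 3.9% | about 5% | 81.7% | 84.1% |
| 50% | 3.2% | about 5% | 82.9% | 87.3% |

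Independent repeat runs agree within 0.2 points for type I error and 0.4 points for power.

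**Detectable difference at 80% power.** With strata, sitting at s = 30% is 14.6 × 1.014 × √0.874 = 13.8 min (13.85 by simulation), against 14.3 as planned. At s = 50% it is 14.6 × 1.014 × √0.79 = 13.2 against 14.1 min. For LPA at s = 50% it is 12.2 × 1.014 × √0.79 = 11.0 against 11.8 min. The 50% case is a 6.5% reduction (5.2% to 7.7% over worksite shares of 36% to 48%).

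**Break-even and downside.** The two tests have equal power at s of about 9% (8% to 11% over the same range). If s = 0, the stated 14.6 and 12.2 min become 14.8 and 12.4 on 17 df, or 14.7 and 12.3 on 19 df.

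**Alternatives.** Region and sector main effects (19 df) give type I error of 5.0% and power of 84.5% and 87.9% at s = 30% and 50% if the two factors do not interact. With arbitrary stratum effects the figures are 4.5% and 4.2%, with power 83.0% and 85.2%.

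Pairs may carry calendar variance, because section 4.2 plans to "rotate the enrollment of sector pairs over the seasons of the full calendar year to help avoid seasonal effects". If pairs, rather than strata, explain 30% of the worksite part, type I error is 3.7%, 4.1% and 5.0% on 22, 17 and 11 df, and power is 81.4% to 81.7% for all three. If pairs explain 50%, power is 82.5%, 83.2% and 85.3%. If they explain nothing, it is 79.9%, 78.7% and 75.9%.

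**The case against.** The strongest reply is that nothing in the plan is invalid. The estimate is unbiased, the test does not over-reject, and sections 12.1 and 12.2 use the same 22 df. Randomisation already delivers the balance the plan wants. All of this stands.

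The gain also depends on a share the documents do not give. Section 12.2 begins "In a baseline-adjusted analysis, let D represent the minimal detectable intervention effect", and adjusting for the baseline outcome may absorb much of what region and sector explain. Below about 9% the planned test has equal or better power. This stands too, and it limits the claim to a conditional one.

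The size is modest. At a 30% share the gain is less than half a minute of sitting, while section 12.2 cites preliminary reductions above 30 min (changes within those studies, not differences between these arms). The 42% rests on one rounded factor applied to both outcomes. With a 20% worksite share, a 30% stratum share gives 4.5% type I error and power of 81.0% against 81.5%, which is negligible.

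Stratum terms do not remove pair-level variance. That is why pairs belong in a sensitivity analysis: as primary terms they would cost about four points of power if they explain nothing.

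One reply fails. The covariate list is worded as open, but 22 df fits only a model without the design factors. Declaring 22 df deliberate would settle the wording and leave the inefficiency in place.

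**Conclusion.** The concern holds in conditional form. The design factors are missing from the primary model and its df, and the planned test is conservative to the extent that they still explain worksite variance after baseline adjustment.

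With a 42% worksite share, stratum shares of 10% to 50% give a true type I error of 4.6% to 3.2%, standard errors about 2% to 11% too large, and up to 4.4 points of power forgone (87.3 − 82.9). Both shares are assumptions: the first is inferred from the dropout factor, the second is unknown. This is a loss of efficiency and a gap in pre-specification, not a threat to validity or to the stated power. Because the remedy is cheap and its worst case is small, it should be made. Confidence in its practical size is medium.

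**What to change.** In section 12.1, state that both primary models include the six region-by-sector strata as fixed effects, with the arm effect tested on 17 df. Region and sector main effects on 19 df are an acceptable alternative: they cost less if strata explain nothing, but stay slightly conservative if the two factors interact. Use the same df in section 12.2 and state the downside there. Add a sensitivity analysis with pair fixed effects on 11 df, to cover calendar differences between pairs.

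The cost is one model term and a matching df in two sections. Region and sector are known for every worksite at randomisation, so no new data are needed. In the worst case the detectable difference is 1.4% (17 df) or 0.7% (19 df) larger.
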